## Planned interim analyses.

Interim analyses will be done after collecting 50% of the data.

## 21. Criteria for terminating the study.

A subject/Patient who is enrolled in the study and for whom study treatment is prematurely terminated will be discontinued from study treatment. After discontinuation/early release from the study, the subject/patient will receive standard-of-care treatment as per the treating clinician. End of Study Efficacy and Safety assessments will be performed, if appropriate and whenever possible.

The study will be terminated when 336 subjects are enrolled, and all data is obtained and documented on the data collection sheet and transferred to Epi-Data program.

## 22. Quality control and quality assurance.

### Preparation quality

- A study approval from the Royal Hospital and Sultan Qaboos University hospital review board obtained.
- Ensure that all required documents (data collection sheet, informed consent), randomization packages are in order and easily accessible for the investigators.
  - o **Investigator's brochure**
- To document that relevant and current scientific information about the investigational product has been provided to the investigator.
  - o **Signed protocol.**
  - o **Informed consent form.**
  - o **Subject Deviation/Unanticipated Problem Case Log.**
  - o **Serious Adverse Event (SAE) Case Log.**
  - o **Withdrawal log.**

- **Nurses and physicians who are involved in the data collection will be trained in the following areas:**
  - o Full description of the attended study and the way to obtain research consent.
  - o Obtaining potassium level from official biochemistry lab result
  - o Preparing Intravenous insulin/Dexstrose 50% + Salbutamol Nebulization.
  - o Measurement of possible side effected and secondary outcomes.

**During research progress regular visits from the principle investigator will be done ensuring the following:**

- Informed Consent forms are properly completed and up to date.
- Participants are appropriately screened and enrolled.
- Inclusion and exclusion criteria are applied properly.
- Randomization procedures are followed, and the blind is maintained.
- Trial assessments and treatment are conducted in compliance with the protocol.
- All source documents are attributable, legible, contemporaneous, original, accurate, and complete.
- Medication dosing and documentation are following the protocol.
- All adverse events and serious adverse events have been documented and appropriately reported to the principle Investigator and Institutional review board.
- Reviewing drug accountability records for completeness and accuracy.
- Checking for protocol deviations/violations that may have occurred.
- Following up on unresolved issues from previous visits.
- Providing, or arranging for, additional staff training in problem areas.

### **23. Data handling and record keeping.**

Subject/patient information obtained because of this study is considered confidential and disclosure to third parties is prohibited. Medical information may be assessed only after approval from the subject/patient to the Investigator. The investigator will not disclose any confidential information regarding subjects during performance of study duties without justifiable reasons. The investigator affirms the subject's right to protection against invasion of privacy. All data collection sheets are collected in a locked and secured box in the emergency department and no access is allowed except for investigators. Any electronic file containing patient data will be protected by a complicated password. No data will be shared through any social platforms including WhatsApp. Data can be shared between investigators only by password protected Google Drive account. After termination of the study and finishing data analysis, data will be stored for a period of 3 year and will be discarded safely and securely.

## 24. Procedures for reporting deviations from the original plan.

- **Definition of Protocol Violation:** A protocol violation refers to any non-compliance with the study protocol, procedures, or approved amendments. This can include, but is not limited to, enrollment of ineligible participants, missed study visits, incorrect drug administration, or failure to obtain informed consent.
- **Identification of Violation:** All study personnel should be vigilant in identifying potential protocol violations. Regular audits and monitoring visits will also serve as a mechanism to identify and address violations.
- **Immediate Action:** Upon identification of a potential protocol violation, immediate corrective action should be taken to ensure the safety and rights of the study participants.
- **Documentation:** All protocol violations, regardless of perceived significance, must be documented in details. This documentation should include the nature of the violation, the date it occurred, the individuals involved, and any corrective actions taken.
- **Notification:** The Principal Investigator (PI) must be informed of all protocol violations within 24 hours of discovery. Depending on the severity and nature of the violation, the Institutional Review Board (IRB) and the study sponsor may also need to be notified.
- **Analysis and Reporting:** The PI, in collaboration with the study team, will analyze the cause of the violation and determine its potential impact on the study's integrity and participant safety. A report detailing the violation, its cause, potential impact, and corrective actions will be submitted to the IRB and study sponsor as required.
- **Preventive Measures:** Based on the analysis, preventive measures will be implemented to avoid recurrence of similar violations. This may include additional training for study personnel, revision of study procedures, or increased monitoring.
- **Follow-Up:** All protocol violations will be reviewed during regular study team meetings to ensure that corrective and preventive actions are effective. Any trends in violations will be addressed promptly.
- **Transparency:** All protocol violations and their resolutions will be transparently reported in the study's final publication to ensure the scientific community is aware of any potential biases or limitations in the study results.

## **Study Protocol Violation Algorithm:**

### **Step 1: Detection**

Monitor study activities regularly.

Review data collection sheets, informed consent forms, and other study-related documents for inconsistencies or missing information.

### **Step 2: Classification**

Classify the detected issue: Is it a minor deviation or a major violation?

Refer to the study protocol for definitions and examples.

### **Step 3: Immediate Action**

For minor deviations: Correct the issue immediately, e.g., obtain a missing signature on a consent form.

For major violations: Pause the affected study activity and ensure the safety of the participant.

### **Step 4: Documentation**

Record the violation in the "Subject Deviation/Unanticipated Problem Case Log."

Include details such as the nature of the violation, date, individuals involved, and corrective actions taken.

### **Step 5: Notification**

Inform the Principal Investigator (PI) within 24 hours of discovery.

If severe, notify the Institutional Review Board (IRB) within 14 working days.

### **Step 6: Analysis**

The PI and study team analyze the cause and potential impact of the violation.

Determine if the violation affects participant safety, data integrity, or participant willingness to continue.

### **Step 7: Report Compilation**

Compile a detailed report of the violation, its cause, potential impact, and corrective actions.

Submit the report to the IRB and any other relevant bodies.

### **Step 8: Preventive Measures**

Implement measures to prevent recurrence based on the analysis.

This could include additional training, revision of study procedures, or increased monitoring.

### **Step 9: Follow-Up**

Review all protocol violations in regular study team meetings.

Address any trends or repeated violations promptly.

### **Step 10: Transparency & Publication**

Ensure all protocol violations and resolutions are transparently reported in the study's final publication.

## **Anticipated Protocol Violations:**

### **Informed Consent Issues:**

1. Missing original signed and dated consent form.
2. Use of an incorrect version of the informed consent form.
3. Missing pages from the executed consent form.
4. Inappropriate documentation of consent, such as missing signatures or the individual obtaining consent not being listed on the IRB approved application.

### **Timing Issues:**

1. The subject/patient falls outside of the window of time indicated by the protocol.

### **Recruitment and Enrollment:**

2. Implementation of unapproved recruitment procedures.
3. Enrollment of participants who do not meet the inclusion and exclusion criteria.

### **Treatment and Assessment:**

1. Incorrect drug administration or dosage.
2. Failure to maintain the study's blind.
3. Not following randomization procedures.
4. Trial assessments not conducted in compliance with the protocol.

### **Documentation and Data Handling:**

1. Inaccurate or incomplete source documents.
2. Medication dosing and documentation not following the protocol.
3. Adverse events not being documented or reported to the PI and IRB.

## **25. Anticipated results**

The antihyperkalemic measure effect of intravenous regular insulin 5units is not inferior to intravenous regular insulin 10 units and there will be fewer side effects.

## 27.Appendix:

### Data collection sheet

Patient hospital ID								
Study Code:								
Demographics								
Hospital								
Location (ED/Inpation)								
Gender								
Age								
DM type								
HTN								
IHD								
ESRD								
Last Dialysis session (if any)								
Other comorbidities								
Home Medications								
Suspected cause of Hyperkalemia								
CBC	Hb:	WBC:	Plat:					
UE	AG:	HCO3:	Creat:	GFR:	Na:	K:		
Mg serum								
Follow up /time line (minutes)	0	60	120					
Potassium								
Blood sugar								
Total amount of Intravenous fluid received during the study period / type of IV fluid								
Other medications administered								
Urine output (if any)								
Needed another antihyperkalemic messures?								
Needed Urgent/Emergent Dialysis?								

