#### Exclusion criteria:

- Cardiac arrest
- Hyperglycemia with random blood sugar 20 mmol/L (13) or with acute diabetic complications like Diabetic Ketoacidosis / Hyperosmolar Hyperglycemic State.
- Hypoglycemia with random blood sugar (RBS)  $\leq 3.89$  mmol/l in Diabetic patients and less than 3 mmol/l in non-Diabetic patients.
- Allergies for any medication in the protocol.
- Pregnancy.
- Hemolyzed potassium level as reported by the main lab.
- Hemolysis, Tumor lysis syndrome, or Rhabdomyolysis due to the ongoing release of potassium.
- Acidosis with a pH less than 7.1 will require Sodium bicarbonate (NaHCO3).
- A patient who will need urgent Furosemide (Lasix), and or dialysis during the study period of 2 hours.
- Refused to participate.

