### Withdrawal criteria

A subject/patient may be withdrawn from the study at any time for any reason and without penalty or prejudice. The following situations may be cause for a subject to be withdrawn from the study:

- Subject did not fulfil the inclusion or exclusion criteria.

- Subject experienced a significant complication, deemed due to the study treatment.
- Subject developed an inter-current illness, condition, or procedural complication that would interfere with continued participation.
- Subject voluntarily withdrew consent.
- Subject was in violation of the protocol.
- Treating Physician decided it is in the best medical interest of the subject to terminate involvement.

Upon occurrence of a serious adverse event or intolerable adverse event, the principal investigator will be notified. If a subject is discontinued from study treatment due to a serious adverse event, the event will be followed until resolution. The investigational staff must fill the withdrawal form (Appendix: [Withdrawal form](#)).

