Other medications as indicated	* →		
Serum Potassium measurement	*		*
Serum Glucose measurement	*	*	*

Figure 1: Schedule for evaluation time-line. ECG: electrocardiography, U&E: Urea and electrolytes, RBS: Random blood sugar, CBC: complete blood count, Mg: Magnesium, PO4: phosphate, VBG: Venous Blood Gas.

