The intention-to-treat (ITT) analysis will include all subjects who provide at least one post-baseline valid measurement. The per-protocol (PP) analysis will only include subjects who have completed the study according to the protocol and who have valid measurements for all time points. Non-inferiority will be concluded if both the ITT and PP analyses show that the difference in means between the two treatment groups is not statistically significant and lies above the margin of -20 units.

Secondary outcomes

Normally distributed continuous variables will be compared between the groups using Independent 't' test or else with Mann-Whitney 'U' test and categorized levels will be compared using chi-square test. The incidence of hypoglycemia will be presented using percentage with 95% confidence interval. A p-value of <0.05 will be considered as statistical significance.

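### Additional potassium-lowering treatment and urgent dialysis are recorded but have no place in the analysis plan, and affected patients can leave the primary set after randomisation

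*Protocol*

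**What the plan says.** **Further treatment is foreseen.** The Protocol's data collection sheet (section 27, Appendix) has the items "Needed another antihyperkalemic messures" and "Needed Urgent/Emergent Dialysis". Both follow the 0/60/120-minute grid, and neither asks for a time or a type. The evaluation schedule in section 7 has a row "Other medications as indicated" that starts at time 0 and continues.

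**Patients can leave after randomisation.** The exclusion criteria include "A patient who will need urgent Furosemide (Lasix), and or dialysis during the study period of 2 hours". The withdrawal criteria list "Subject did not fulfil the inclusion or exclusion criteria" and "Treating Physician decided it is in the best medical interest of the subject to terminate involvement". For patients discontinued early, Protocol section 21 says "End of Study Efficacy and Safety assessments will be performed, if appropriate and whenever possible".

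**The SAP does not mention further treatment or dialysis.** The primary model adjusts for baseline potassium only. Potassium is measured at 0 and 120 minutes, so there is one post-baseline value. The analysis sets are each described twice:

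| Set | SAP, Populations | SAP, Statistical analysis (Primary outcome) |
|---|---|---|
| ITT | all randomised subjects | only subjects with at least one valid post-baseline value |
| PP | complete cases | will "only include subjects who have completed the study according to the protocol" and have valid values at all time points |

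Non-inferiority requires both sets to meet the rule, with a margin given as minus 20 units.

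**The concern.** The need for more treatment is direct evidence that the assigned treatment was not enough. In a superiority trial, blurring that evidence usually costs power. In a non-inferiority trial it can produce the claim. If patients on 5 units need more help before the 120-minute sample, and that help lowers their potassium or removes them from the comparison, 5 units will look closer to 10 units than it is. The plan sets no rule in advance, so the handling could be chosen after data have been seen, and an interim analysis at 50% of the data is planned.

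**Working it through.** **Step 1. Follow a patient who is treated further before 120 minutes.**

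- *Sampled at 120 minutes.* The value enters ITT under either definition. The model has no term or rule for the extra treatment, so its effect is attributed to the insulin dose.
- *Withdrawn and not sampled.* The physician-decision reason allows withdrawal, and section 21 makes the final assessment conditional. With a single post-baseline time point, a missed sample removes the patient from ITT as the SAP's Primary outcome text defines it, although Populations says all randomised.
- *Reclassified as ineligible.* The furosemide/dialysis exclusion is worded by need within the 2-hour study period, and unmet eligibility is a withdrawal reason. Read together, these allow dialysis after randomisation to become an exclusion after randomisation.
- *In PP.* If further treatment counts as being within the protocol, PP keeps the affected value. If it does not, PP drops the patient. Neither reading corrects the estimate.

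**Step 2. Size if the extra treatment is ignored.**

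Inputs from the documents: SD 0.62, 160 per arm, one-sided alpha 0.025. Assumptions: a margin of 0.2 mmol/L (the sample-size effect figure, because minus 20 units does not fit a mmol/L endpoint); an excess of 5 or 10 percentage points with 5 units; an extra fall of 0.3 or 0.6 mmol/L.

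The 160 per arm is taken as stated. The plan's own inputs with a 0.2 margin give 2 × 0.62² × (1.960 + 1.282)² / 0.2² ≈ 202 per arm. That is a separate matter.

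SE = 0.62 × √(2/160) = 0.0693

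Shift = excess proportion × extra fall

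False non-inferiority at a true deficit of 0.2 = P(Z > 1.96 − shift/SE)

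| Excess | Extra fall (mmol/L) | Shift | 1.96 − shift/SE | False non-inferiority |
|---|---|---|---|---|
| 0 | any | 0 | 1.96 | 2.5% |
| 5 points | 0.3 | 0.015 | 1.74 | 4.1% |
| 5 points | 0.6 | 0.030 | 1.53 | 6.3% |
| 10 points | 0.3 | 0.030 | 1.53 | 6.3% |
| 10 points | 0.6 | 0.060 | 1.09 | 13.7% |

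**Step 3. Size if the patients are removed.**

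Assume reductions distributed N(0.6, 0.62) with 10 units and N(0.4, 0.62) with 5 units, a true deficit of 0.2.

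- Removing everyone whose reduction is below −0.4 takes out 5.3% and 9.8%. The apparent deficit falls to about 0.15, and false non-inferiority rises to about 12%.
- If removal is only weakly tied to response (correlation 0.5; 1.9–10% removed with 10 units, 2.7–13% with 5 units), the apparent deficit is 0.194 to 0.184 and the error is 3.1% to 4.1%.

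**Step 4. Would imputing zero reduction be a safe remedy?**

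Use the first scenario of step 3 and set those below −0.4 to zero. The arm mean becomes μΦ(a) + 0.62φ(a), with a = (μ + 0.4)/0.62.

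- 10 units: a = 1.613, mean = 0.6 × 0.9466 + 0.62 × 0.1087 = 0.635
- 5 units: a = 1.290, mean = 0.4 × 0.9015 + 0.62 × 0.1735 = 0.468

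The difference is 0.167, against a true 0.20. Zero is better than these patients' own values, so this imputation also shrinks the deficit.

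**The case against.** The strongest reply is that the design leaves little room for differential early treatment. No potassium is scheduled between 0 and 120 minutes, the physician is meant to be blinded to dose, both arms receive salbutamol, and foreseeable need for urgent furosemide or dialysis is excluded at screening. This stands, and it limits the likely size. It does not supply the missing rule.

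Analysing the observed value whatever else was given is also a legitimate treatment-policy estimand. That is true, but the SAP does not declare it, and it is not conservative for non-inferiority.

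Four stronger readings are tempting and are not supported:

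- *That the sheet documents treatment before 120 minutes.* The two fields are untimed. They fit equally well a decision made after the 2-hour result, which would not affect the endpoint.
- *That PP removes these patients.* Other medications are allowed from time 0, and one of the two PP definitions is simply complete cases. PP may well keep them.
- *That a large error inflation should be expected.* No rates are given. Nor do the documents give an effect for further treatment: 0.6 mmol/L is borrowed from the target reduction for study treatment.
- *That the exclusion will be applied after randomisation.* It is an eligibility criterion, checked at screening, and the withdrawal reasons are permissive. The wording allows that use but does not direct it.

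**Conclusion.** The point holds in a conditional form. The plan collects information on further treatment and dialysis, has no rule for it, and gives two inconsistent ITT definitions, one of which lets such patients leave the primary set. If further treatment before the 120-minute sample is more frequent with 5 units, both routes favour non-inferiority, and requiring ITT and PP to agree does not prevent it.

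The size is unknown. The illustrative 4–14%, against a nominal 2.5%, rests on the assumed margin, excess and extra fall in step 2. With equal rates and effects, ignoring further treatment causes no bias. Early further treatment may be uncommon. The change is worth making because it is cheap and closes a choice that would otherwise be open after data are seen. The evidence does not show that the trial's conclusion would be wrong.

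**What to change.** 1. **Analysis set (SAP).** Keep all randomised patients in ITT. Seek the 120-minute sample from everyone, including those treated further or withdrawn. For analysis, apply the furosemide/dialysis exclusion only to need known before randomisation. Reconcile the Protocol's exclusion and withdrawal criteria with the two ITT and two PP definitions in the SAP.
2. **Data and reporting.** Add time and type to the two fields on the collection sheet. Report additional potassium-lowering treatment or dialysis before the 120-minute sample by arm, with the risk difference and 95% CI.
3. **Estimand and sensitivity.** State that the primary analysis uses observed values regardless of additional treatment. Add a supportive analysis that treats these patients unfavourably, such as composite failure, worst rank or a range of imputed values. Do not make a single zero-reduction imputation a condition of the conclusion (step 4).

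Cost: a small form change, SAP wording, one table and one supportive analysis. The existing sheet alone is not enough, because it cannot place events before or after the 120-minute sample. No change to patient treatment is proposed.

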## Medications administration form:

### Medications administration card

(Insulin 5 units group)

- The doctor **must not know** the dose of insulin received by the patient.
- Give the patient the following medications:
  - Insulin Regular 5 units with Dextrose 50 ml of 50 % concentration intravenously (IV) over 30 minutes.
  - Salbutamol 10 mg Nebulization over 15 minutes.

Please repeat potassium level after 120 minutes from the time insulin/dextrose infusion

Repeat RBS: 60 and 120 minutes.

	60 minutes	120 minutes
Serum Potassium measurement		*
*RBS via glucometer	*	*

- If a patient become hypoglycemic (random blood sugar (RBS)  $\leq$  3.89 mmol/l in Diabetic patients and less than 3 mmol/l in non-Diabetic patients) inform the Doctor/Research assistant.
- Example: if you start insulin/Dextrose at 02:00 the infusion till 02:30 so repeat RBS at 03:00 and 04:00. Repeat U&E at 04:00.
- \*RBS: Random blood sugar. U&E: urea and electrolytes.

---

---

### Medications administration card

(Insulin 5 units group)

- The doctor **must not know** the dose of insulin received by the patient.
- Give the patient the following medications:
  - Insulin Regular 5 units with Dextrose 50 ml of 50 % concentration intravenously (IV) over 30 minutes.
  - Salbutamol 10 mg Nebulization over 15 minutes.

Please repeat potassium level after 120 minutes from the time insulin/dextrose infusion

Repeat RBS: 60 and 120 minutes.

	60 minutes	120 minutes
Serum Potassium measurement		*
*RBS via glucometer	*	*

- If a patient become hypoglycemic (random blood sugar (RBS)  $\leq$  3.89 mmol/l in Diabetic patients and less than 3 mmol/l in non-Diabetic patients) inform the Doctor/Research assistant.
- Example: if you start insulin/Dextrose at 02:00 the infusion till 02:30 so repeat RBS at 03:00 and 04:00. Repeat U&E at 04:00.
- \*RBS: Random blood sugar. U&E: urea and electrolytes.

Study Flow chart:

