### Control Group

The patient will receive 10 U of regular insulin + Dextrose 50% over 30 minutes + salbutamol nebulization 10mg in 3ml normal saline over 15min, calcium gluconate will be given according to the physician responsible about the case.

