## **6. Randomization**

When a patient has hyperkalemia ( $K \geq 5.5$  mEq/L) our doctor/investigator will come to explain the research to the patient/relatives and after explaining all details a written consent will be signed. Our doctor/investigator will take a random envelope from the study box to randomize the patient between 5 units or 10 units of insulin with 50 ml of 50% Dextrose and salbutamol Nebulization. The doctor will take the envelope code and place it on the data collection sheet without looking into the instructions. The Doctor will give the nurse that envelope. Each envelope will have instructions about the medications administration route and dose (see appendix: [medications administration form](#)). The Nurse will administer the medications with the documentation of starting time. Then our doctor will follow the patients and lab results for 2 hours based on the ACEP and Ministry of Health/Royal hospital protocol.

Randomization codes will be done by an online free site for having unique codes (<https://www.randomcodegenerator.com/en/generate-codes>). Eligible participants after obtaining consent will be randomly assigned to either 5 units of Intravenous insulin or 10 units of intravenous insulin. The researcher and patient will not know the dose of insulin administered.

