## **7. Study flow**

The study protocol will be for a total of 2 hours. All groups will follow the same path except the dose of insulin administered. After the result of potassium level ( $\geq 5.5$  mEq/L) patient will be screened for inclusion and exclusion criteria at the same time all other medications except insulin can be administered as the doses are fixed. Eligible patient will have to sign a

written consent if they agreed to be involved in our study. The initial data and basic labs will be collected before starting the study protocol. The incharge doctor/investigator will take the random code and write it on the data collection sheet of that patient from already prepared list/code and give the assigned nurse the medications administration card/form (see appendix: [medications administration form](#)).

Every patient will receive:

- Potassium lowering agent:
    - Intravenous Regular insulin 5 units **OR** 10 units with Glucose 50% water 50 ml over 30 minutes according to the randomization.
    - Salbutamol nebulization 10 mg in 3ml normal saline over 15 minutes.
  - The physician will decide the need of cardiac stabilizing agents (e.g Calcium Gluconate) as indicated by the physician in-charge of the patient.
- Please see [study flow chart](#) in the attachment.

5 Units insulin group	10 units insulin group
Medications to be administered: • IV Insulin Regular 5 units with Dextrose 50 % 50 ml over 30 minutes. • Salbutamol 10 mg NEB over 15 minutes.	Medications to be administered: • IV Insulin Regular 10 units with Dextrose 50 % 50 ml over 30 minutes. • Salbutamol 10 mg NEB over 15 minutes.

Figure 1: Treatment. RBS: Random Blood sugar. IV: Intravenous. NEB: Nebulization.

Initial investigations will include:

ECG, Urea and electrolytes, Creatinine, eGFR, Random blood sugar, complete blood count, Magnesium level, bone profile, phosphate level, will be attached if not sent before.

Repeated labs will be with these frequencies:

**Potassium** level: 0 and 120 minutes from medications administration time.

**Blood sugar**: 0, 60 and 120 minutes from medications administration time.

The study will be over at 2 hours (120 minutes) or by patient decision to withdraw from the study.

	0	Post involvement	
		60	120
Timeline (minutes) from medications administration	0	60	120
Eligibility screen	*		
Consent	*		
Randomization	*		
Basic labs: ECG, U&E, RBS, CBC, Mg, bone profile, PO4, VBG.	*		
Study Medication administration	* →		

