#### Method for Application of Intravenous Regular Insulin 10 units

1. Perform hand hygiene and don clean gloves.
2. Draw the 10 units of regular insulin.
3. Mix it with 50ml of dextrose 50%.
4. Connect to placed venous cannula.
5. Run it no less than 5 seconds (proposed 30 minutes)
6. Disconnect and discard all materials in their proper disposal bins.

7. Remove gloves and preform hand hygiene.

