### Each package contains:

- **Envelope with:**
  - o Data collection sheet with unique generated number.
  - o Consent form.
  - o Instructions sheet
  - o Medication administration form (for the nurses).

Blood investigation will be sent to biochemistry lab for potassium level and other investigations, and it's the only acceptable way in the study. The study investigators will verify that study treatments are received intact and in the correct amounts.

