## Randomization

1. Open study envelope.
2. Take the included code in that envelope and stick it to the patient data collection sheet.
3. Give medication instructions card to the nurse in-charge of the patient

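### The appendix prints the nurse's medication card twice for the 5-unit arm and contains no card for the 10-unit arm

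*Protocol*

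**What the plan says.** Protocol section 6 (Randomization) says of the envelopes: "Each envelope will have instructions about the medications administration route and dose", and refers the reader to the medications administration form in the appendix. Section 9 lists that form, for the nurses, among the contents of each package. The flow chart in the appendix then has the investigator "Give medication instructions card to the nurse in-charge of the patient".

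The appendix (section 27, Medications administration form) prints two cards. Each is labelled for the 5-unit group and orders "Insulin Regular 5 units with Dextrose 50 ml of 50 % concentration intravenously (IV) over 30 minutes".

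The control dose is defined correctly elsewhere:
- Section 5, Control Group: "The patient will receive 10 U of regular insulin + Dextrose 50% over 30 minutes".
- Section 7, treatment table: "IV Insulin Regular 10 units with Dextrose 50 % 50 ml over 30 minutes".
- Section 8, method for the 10-unit dose: "Draw the 10 units of regular insulin".
- The flow chart shows a 10-unit branch, and section 9 (Packaging and Labelling) plans packages for both doses.

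Three smaller points concern the same instructions. Step 2 of the salbutamol method in section 8 names insulin as the drug to take, at 10 mg. The SAP (Study design) gives the insulin/dextrose over 15 minutes in both arms. Step 5 of both insulin methods in section 8 sets a minimum of 5 seconds, with 30 minutes as the proposed time.

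**The concern.** The card turns the allocation into a dose. Under section 6 the doctor passes the envelope on without reading the instructions, and the card itself says that the doctor must not know the dose. The nurse therefore acts on the card with no prescriber checking it. The data collection sheet has no field for the insulin dose given, and section 6 asks the nurse to record only the start time. A wrong card would not show up in the study data.

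The direction of such an error matters in a non-inferiority trial. Control patients given 5 units would make the arms alike, which moves the result toward the conclusion the trial hopes to reach. It would also remove the contrast for hypoglycemia, a secondary outcome and the main argument for the lower dose.

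**Working it through.** There is no planned figure to reproduce. The check is a comparison of text, with counts.

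**Cards.**

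| Item | First card | Second card |
|---|---|---|
| Group in heading | 5 units | 5 units |
| Insulin ordered | 5 units, 30 min | 5 units, 30 min |
| Salbutamol | 10 mg, 15 min | 10 mg, 15 min |
| Repeat potassium | 120 min | 120 min |
| Repeat blood sugar | 60 and 120 min | 60 and 120 min |

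Cards for 5 units: 2 of 2. Cards for 10 units: 0 of 2.

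**Could a 10-unit card be lost from the copy?** The contents list puts the form on page 28 and the study flow chart on page 29. The second card runs straight into the flow chart heading. There is no gap at this point for a third card.

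**Packages that need the missing card.** Section 20 gives 168 per arm and 336 in total: 168 / 336 = 50%.

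**Dose contrast.** Planned: 10 - 5 = 5 units. With both cards used as printed: 5 - 5 = 0 units.

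**Checks in the protocol that might catch it.**
- Section 9: investigators verify that study treatments arrive intact and in the right amounts.
- Section 22: randomization packages must be in order, staff are trained in preparing the insulin, and visits review randomization, dosing and drug accountability.
- Section 24: a wrong dose is listed as an anticipated violation.

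None of these names a comparison of the dose on the card with the allocation. Each package also holds an "Instructions sheet", but its content is not shown, so it cannot be counted for or against.

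**Salbutamol step.** Insulin is named once (section 8, salbutamol method, step 2). Salbutamol 10 mg is given in six places: Control Group, Intervention Group, section 7, both cards and the flow chart. The step stands under a salbutamol heading, so the intended drug is clear.

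**Infusion time.** Thirty minutes appears in seven places: the Aim and the Intervention in section 1, Control Group, Intervention Group, section 7, and both cards. Fifteen minutes appears in the SAP study design, once for each arm. The 5-second minimum in section 8 is looser than the rest but does not contradict it. Every version is the same in both arms, so no between-arm bias follows.

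**The case against.** The strongest reply is that this is a clerical slip in an appendix. Both cards fit on one page and are identical, so the page may be a cut sheet holding two copies of one specimen. No sentence promises one card per arm. The 10-unit arm is defined correctly in several sections, packages carry numbers tied to the arm, and staff are trained and monitored. For harm to follow, someone would have to put a card visibly headed for the 5-unit group into control packages without noticing, in a trial whose only contrast is 5 against 10 units.

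Much of this stands. The cause of the duplication cannot be settled from the text, no misdosing is shown, and the existing checks lower the risk. The 50% is simply the allocation share, and the 0-unit contrast describes the extreme case. The section 8 infusion wording is a matter of tidiness.

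It does not remove the point. On the specimen reading the control arm's card is still missing, and replacing one duplicate gives one card per arm on either reading. The checks on dosing do not supply the card, and the protocol makes this form the order that the nurse follows.

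**Conclusion.** The point holds. The appendix is wrong as written: two 5-unit cards, no 10-unit card, and the missing one serves 168 of 336 planned patients. The trial is not invalid on this account, because the control dose is correctly defined elsewhere. The loss of contrast from 5 units to 0 assumes that both cards were packed and followed exactly as printed. The documents give no misuse rate, so no effect on the error rate of the non-inferiority conclusion is claimed. The salbutamol wording and the SAP infusion time are real but lesser errors. This should be fixed because the form is an operative dosing instruction used under blinding and the correction costs almost nothing.

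**What to change.** - Replace the second card with one headed for the 10-unit group that orders 10 units of regular insulin with 50 ml of 50% dextrose intravenously over 30 minutes. Leave its other lines unchanged.
- If envelopes have already been packed, compare the dose on each card with the allocation list, and record the result.
- In the salbutamol method (section 8, step 2), change the drug to salbutamol.
- In the SAP study design, change the insulin/dextrose time from 15 to 30 minutes in both arms.
- For consistency, state 30 minutes in step 5 of both insulin methods in section 8.

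The cost is one card, one word, two SAP sentences and one line in each insulin method, plus a check of any packed envelopes. Design, sample size and analysis do not change.
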